### 8.3.3 CLASSIFICATION OF AN ADVERSE EVENT

#### 8.3.3.1 SEVERITY OF EVENT

A clinical determination will be made of the intensity of an adverse event. The severity assessment for a clinical adverse event must be completed using the following definitions as guidelines:

Mild	Awareness of sign or symptom, but easily tolerated
Moderate	Discomfort enough to cause interference with usual activity
Severe	Incapacitating with inability to work or do usual activity

#### 8.3.3.2 RELATIONSHIP TO STUDY INTERVENTION

A determination will be made of the relationship (if any) between an adverse event and the study drug or study procedure, as applicable. A causal relationship is present if a determination is made that there is a reasonable possibility that the adverse event may have been caused by the drug or study procedure. Causality should be assessed using the following categories:

- **Unrelated:** Clinical event with an incompatible time relationship to study drug administration, and that could be explained by underlying disease or other drugs or chemicals or is incontrovertibly not related to the study drug.
- **Unlikely:** Clinical event whose time relationship to study drug administration makes a causal connection improbable, but that could plausibly be explained by underlying disease or other drugs or chemicals.
- **Possible:** Clinical event with a reasonable time relationship to study drug administration, but that could also be explained by concurrent disease or other drugs or chemicals.
- **Probable:** Clinical event with a reasonable time relationship to study drug administration, and is unlikely to be attributed to concurrent disease or other drugs or chemicals.
- **Very Likely/Certain:** Clinical event with plausible time relationship to study drug administration, and that cannot be explained by concurrent disease or other drugs

or chemicals.

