#### 8.3.4.1 DOCUMENTATION AND REPORTING OF ADVERSE EVENTS

AEs should be reported and documented in accordance with the procedures outlined below. All AEs occurring during the study must be documented on the relevant CRF pages. The following data should be documented for each AE:

- Description of the symptom event
- Classification of 'serious' or 'not serious'
- Severity
- Date of first occurrence and date of resolution (if applicable)
- Action taken
- Causal relationship
- Outcome of event (unknown, recovered, not yet recovered, recovered with sequelae, death [with date and cause reported])

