- Eyelid margin erythema/telangiectasias at day14, month 1, month 1.5, and month 3
- Corneal and conjunctival staining (0 to 5 scale) at each visit

*Safety:* Safety measures will be analyzed using the safety population. Medical Dictionary for Regulatory Activities (MedDRA) nomenclature will be used to code adverse events. Incidence rates of each treatment-emergent adverse event will be summarized by primary system organ class and preferred term. Summary tables will be generated for all treatment-emergent adverse events regardless of causality as well as for those considered to be treatment-related.

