11.1 ALL ADVERSE EVENTS

Summaries of incidence rates of individual TEAEs by System Organ Class (SOC) and Preferred Term (PT) will be prepared. Because a subject may experience more than one AE, summaries will provide both the number of subjects experiencing at least one event and the number of events within a reporting period. Percentages provided will be the percent of subjects experiencing one or more adverse events. In addition, incidence of TEAEs will be presented by severity (mild, moderate, severe) and by relationship (unrelated, unlikely, possible, probable, very likely/certain) to investigational treatment. Subjects experiencing an event within a given PT and SOC more than once will be counted under the maximum severity/relationship experienced.

A TEAE is any AE that is new in onset or was aggravated in severity or frequency following the application of first study drug, up to 30 days of receiving the last study drug. If the start date of any AE is incomplete or missing, the event will be assumed to be a TEAE, unless the incomplete start date (month and/or year) or the stop date (complete or incomplete) clearly indicates that the event started prior to the study drug.

A listing of all adverse events will include the subject number, AE number, the AE SOC and PT, the severity of AE, whether or not the AE is classified as serious (SAE), the relationship of the AE to the study intervention, the action taken, the outcome, and the adjudication status.

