11.4 DRUG OR PROCEDURE RELATED ADVERSE EVENTS

Summaries of incidence rates of drug and procedure related AEs by SOC and PT will be prepared. Related events include those classified as possible, probable, very likely/certain. Events classified as unrelated or unlikely will be considered not related. Summaries will provide both the number of subjects and the number of events within a reporting period. Percentages provided will be the percent of subjects experiencing one or more study intervention related adverse events. Data listings of drug and procedure related AEs will also be provided, displaying details of the event(s) captured on the CRF.

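### Protocol 8.3.3.2 accepts drug or procedure as the cause but grades events only against the drug, so the treatment-related adverse-event table is not clearly limited to drug-related events

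*Protocol*

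**What the plan says.** Protocol 8.3.3.2 asks for one determination of the "relationship (if any) between an adverse event and the study drug or study procedure, as applicable". It counts a causal relationship as present when there is a "reasonable possibility that the adverse event may have been caused by the drug or study procedure". The five categories that follow, from unrelated to very likely/certain, are worded around study drug. The middle one, possible, begins "Clinical event with a reasonable time relationship to study drug administration, but that could also be explained by concurrent disease or other drugs". No category mentions a procedure.

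Protocol 8.3.4.1 lists what to document for each event. Causality is one line, "Causal relationship", not split by cause.

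On reporting, Protocol 9.4.1 promises: "Summary tables will be generated for all treatment-emergent adverse events regardless of causality as well as for those considered to be treatment-related". The synopsis repeats this, and Table 3–1 lists treatment-related tables among the safety endpoints.

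SAP 11.1 tabulates treatment-emergent events by "relationship (unrelated, unlikely, possible, probable, very likely/certain) to investigational treatment". SAP 11.3 gives the relationship of serious events to drug/procedure in combined form. SAP 11.4, whose title names drug or procedure, says: "Summaries of incidence rates of drug and procedure related AEs by SOC and PT will be prepared". It counts possible and above as related, and reports one percentage, labelled as study-intervention related.

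**The concern.** The study's objective is the safety and tolerability of the ointment against vehicle. The reader of a treatment-related table will take it as the investigators' view of what the ointment did. The plan does not secure that reading: the causality question admits procedures, the scale does not mention them, and the SAP summary names both causes under one percentage.

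The point has practical weight because the assessments act on the same tissue as the drug. The Schedule of Activities places fluorescein, lissamine green and meibomian gland evaluation at all four post-baseline visits, and Schirmer without anaesthesia at two of them (months 1 and 3). A reaction to any of these could look like ocular irritation from the ointment. If such reactions are counted as treatment-related, both arms' rates rise and a real excess on active drug looks smaller.

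**Working it through.** The documents state no figure on relatedness, so there is none to reproduce. The check is a comparison of the text, followed by an illustration on assumed rates.

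**Text comparison**

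1. *Question against scale (Protocol 8.3.3.2).* Irritation from a Schirmer strip is causally related under the opening sentences. Under the categories, the grade depends on the time relationship to study drug and on whether disease or other drugs or chemicals explain the event. A dye may pass as a chemical; gland expression and a paper strip are neither. With dosing twice weekly and 2 or 3 rest days between doses (Protocol 4.2.2), most on-treatment events follow a dose fairly closely. Read literally, a mechanical reaction could be graded probable. It could equally be graded unrelated, as incontrovertibly not due to the drug. Two investigators could grade the same event in opposite ways and both comply.
2. *Rating against tables.* The protocol lists one item per event. SAP 11.1 calls the five levels relationship to treatment; SAP 11.4 uses the same levels for drug and procedure together. Neither document says which cause defines treatment-related.
3. *Event scope.* The protocol's promise concerns treatment-emergent events. SAP 11.4 says AEs, without that limit. SAP 11.1 counts events as treatment-emergent only after first study drug, so reactions to screening or baseline procedures before that dose drop out of the 11.1 tables but could enter 11.4.

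**Illustration (all rates are assumptions)**

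Let d be the proportion of an arm with a drug reaction, and q the proportion with a procedure reaction, equal in both arms and independent of d. If every procedure reaction were counted as related:

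- observed proportion p = 1 − (1 − d)(1 − q)
- difference = (1 − q) × (d active − d vehicle)

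About 30 patients at 1:1 gives about 15 per arm, so one patient is 1/15 = 6.7 points. The last column is the lost difference × 15.

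| d active / vehicle | q | Active | Vehicle | Difference (points) | Ratio | Loss, in patients of 15 |
|---|---|---|---|---|---|---|
| 20% / 5% | 0 | 20% | 5% | 15.0 | 4.0 | – |
| | 10% | 28% | 14.5% | 13.5 | 1.9 | 0.23 |
| | 20% | 36% | 24% | 12.0 | 1.5 | 0.45 |
| | 30% | 44% | 33.5% | 10.5 | 1.3 | 0.68 |
| 30% / 5% | 0 | 30% | 5% | 25.0 | 6.0 | – |
| | 10% | 37% | 14.5% | 22.5 | 2.6 | 0.38 |
| | 30% | 51% | 33.5% | 17.5 | 1.5 | 1.13 |
| 40% / 10% | 0 | 40% | 10% | 30.0 | 4.0 | – |
| | 10% | 46% | 19% | 27.0 | 2.4 | 0.45 |
| | 30% | 58% | 37% | 21.0 | 1.6 | 1.35 |

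Example, first set at q = 10%: active 1 − 0.80 × 0.90 = 0.280; vehicle 1 − 0.95 × 0.90 = 0.145.

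For scale, Fisher's exact test (two-sided 0.05, 15 per arm) has power of 27.5% for 30% versus 5% and 32.5% for 40% versus 10% without any pooling. At q = 30% these fall to 7.4% and 10.5%. SAP section 11 describes no such test, so the table would be read by eye.

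**The case against.** The strongest reply is that the scale itself is anchored to study drug. An investigator who follows the category text can grade a clear dye, strip or expression reaction as unrelated or unlikely, and SAP 11.4 counts both as not related. Self-application at bedtime, apart from clinic procedures, helps that judgement. This stands: it is wrong to infer that procedure reactions have no proper place on the scale, or that mixing is certain. What remains is that the opening sentences tell the same investigator the opposite.

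Second, a reader might infer that the two causes cannot be separated in any table. The documents do not support that. Section 8.3.4.1 lists data elements and is not a form layout. The SAP was written against case report forms issued on 25 June 2020, which are not available here and may hold separate fields. SAP 11.1 is worded for treatment only, so mixing there is a risk and not a stated rule. SAP 11.4 could mean two summaries, although its single percentage tells against that.

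Third, a reader might infer that the rating decides which events are reported as suspected unexpected serious reactions. No section says so. Section 8.3.6.1 defines such reactions by relation to study drug administration, and 8.3.2.1 requires serious events to be reported whatever their relationship.

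Fourth, the vehicle comparison does not rest on this table. All-causality treatment-emergent summaries are planned, and tolerability has its own questionnaire, which after baseline refers to the last evening dose. This stands and limits the consequence.

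**Conclusion.** The point holds as an internal contradiction in Protocol 8.3.3.2 that carries into SAP 11.3 and 11.4. As documented, the promised treatment-related table is not clearly limited to drug-related events.

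The consequence is dilution of a true drug-vehicle difference. A reader might infer a directional bias or a false signal; identical procedures in both arms do not support that.

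The size is unknown and, at about 15 per arm, probably small in absolute terms: under one patient for 20% versus 5%, and up to about 1.4 patients at the top of the assumed range. Ratios move more, for example from 4.0 to between 1.9 and 1.3. These figures assume equal and independent procedure reactions, all graded as related. Since some would be graded unrelated, they overstate the effect for any given q. The all-causality tables are not affected.

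**What to change.** - **Protocol 8.3.3.2 and 8.3.4.1:** record causality to study drug and causality to study procedure as two items, each with its own category wording. If the case report form already holds both, confirm this and name the fields in the SAP.
- **SAP 11.1, 11.3 and 11.4:** define treatment-related by the study-drug rating only, limit the treatment-related table to treatment-emergent events as Protocol 9.4.1 promises, and tabulate procedure-related events separately.

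The cost is at most one added form item and a few sentences in each document. The downside is one more judgement per adverse event for the masked investigator.

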### 8.3.3.3 ACTION TAKEN

The investigator will describe the action taken in the appropriate section of the CRF, as follows:

- None
- Study drug stopped
- Study drug temporarily interrupted
- Concomitant medication
- Other, specify.

### 8.3.4 TIME PERIOD & FREQUENCY FOR EVENT ASSESSMENT AND FOLLOW-UP

All investigators should follow up subjects with AEs until the event is resolved or until, in the opinion of the investigator, the event is stabilized or determined to be chronic. Details of AE resolution must be documented in the CRF.

Subjects should be followed up for 30 days (check time limit with sponsor) after receiving the last dose of study drug, and any AEs that occur during this time should be reported according to the procedures outlined above.

#### 8.3.4.1 DOCUMENTATION AND REPORTING OF ADVERSE EVENTS

AEs should be reported and documented in accordance with the procedures outlined below. All AEs occurring during the study must be documented on the relevant CRF pages. The following data should be documented for each AE:

- Description of the symptom event
- Classification of 'serious' or 'not serious'
- Severity
- Date of first occurrence and date of resolution (if applicable)
- Action taken
- Causal relationship
- Outcome of event (unknown, recovered, not yet recovered, recovered with sequelae, death [with date and cause reported])

### 8.3.5 REPORTING EVENTS TO PARTICIPANTS

When necessary for the safety and proper treatment of the patient, the investigator can unmask the patient's treatment assignment to determine which treatment has been assigned and institute appropriate follow-up care. The Randomization and Unblinding Plan should be followed in any instance of request for unblinding. When possible, the sponsor (Azura Ophthalmics) should be notified prior to unmasking study medication. The investigator should inform the sponsor (Azura Ophthalmics) of the unmasking if there is no notification prior to the unmasking.

The reason for breaking the code must be recorded in the patient's source documents.

A report of the results of this study may be published, sent to the appropriate health authorities in any country in which the study drug may ultimately be marketed, and published in part as required by appropriate health authorities (e.g., Clinical Trials posting and disclosure), but the patient's name will not be disclosed in these documents.

Patients will be informed that the study is posted and the results eventually disclosed by appropriate health authorities (e.g., Clinical Trials posting or freedom of information by the FDA).

### 8.3.6 EVENTS OF SPECIAL INTEREST

#### 8.3.6.1 UNEXPECTED ADVERSE REACTION DEFINITION

An unexpected adverse reaction is any untoward and unintended response that is related to the administration of the study drug at any dose that is not consistent with the applicable product information (e.g., investigators brochure for an unauthorized investigational medicinal product or summary of product characteristics for an authorized product).

All suspected unexpected serious adverse reactions (SUSARs) will be the subject of expedited reporting. The sponsor and/or CRO shall ensure that all relevant information about a SUSAR that is fatal or life-threatening is reported to the relevant competent authorities and IEC/IRB within 7 days after knowledge by the sponsor of such a case and that relevant follow up information is communicated within an additional 8 days. All other SUSARs will be reported to the relevant competent authorities and IEC/IRB within 15 days after knowledge by the sponsor of such a case. All investigators should follow up SUSARs until the event is resolved or until, in the opinion of the investigator, the event is stabilized or determined to be chronic. Post study SUSARs that occur after the subject has completed the clinical study must be reported by the investigator to the sponsor.

### 8.3.7 REPORTING OF PREGNANCY

If a female becomes pregnant during the study, the investigator will notify Azura Ophthalmics

immediately after the pregnancy is confirmed and the patient will be exited from the study after appropriate safety follow-up. The investigator will (1) notify the patient's physician that the patient was being treated with an investigational drug, and (2) follow the progress of the pregnancy. The investigator must document the outcome of the pregnancy and provide a copy of the documentation to Azura Ophthalmics.

## 9 STATISTICAL CONSIDERATIONS

The statistical analysis plan (SAP) will provide a detailed description of the planned statistical analysis.

### 9.1 SAMPLE SIZE DETERMINATION

**Sample Size Calculation:** Estimates for sample size calculations are from the first interim analysis from Azura Clinical Protocol AZ201801. The standard deviation for MGS was 3.35 units for an ineffective dose and 9.48 units for the high dose. A sample size of 12 subjects per group will have 90% power to detect a difference of 10.4 units between the active treatment group and the vehicle group using a two-sample t-test at a significance level of 0.05. The standard deviation for Total OSDI was 13.01 units for an ineffective dose and 6.79 units for the high dose. A sample size of 11 subjects per group will have 90% power to detect a difference of 15.9 units between the active treatment group and the vehicle group using a two-sample t-test at a significance level of 0.05.

**Multiplicity Consideration:** To address the multiple primary endpoints defined in this study, the primary endpoints have been prioritized into a hierarchical structure. In order to test the primary symptom endpoint of Total OSDI, the primary sign endpoint of MGS must be statistically significantly higher in the 0.5% AZR-MD-001 treatment group compared to the vehicle treatment group using a two-sided significance level of 0.05. Using this strategy, the family-wise Type I error rate will be maintained at the 0.05 significance level for the two primary endpoints.

### 9.2 POPULATIONS FOR ANALYSES

The safety population will include all treated patients. For safety variables, patients in the safety population will be analyzed by the treatment actually received. The modified intent-to-treat (mITT) population will be comprised of all patients randomized and, have values at randomization, and at least 1 post-randomization value for MGS at a regularly scheduled visit (i.e., Day 14 or Month 1). All patients in the mITT population will be analyzed by the treatment received. This population will be used for the primary and the secondary efficacy analyses.

The method of Last Observation Carried Forward (LOCF) will be used for efficacy on the mITT

population. In these analyses, non-missing values recorded at visit 3 (i.e., Day 14) or later will be used to replace missing data at visits where data are not recorded.

Additional imputation methods will be used for sensitivity analysis and will be outlined in the Statistical Analysis Plan (SAP).

### 9.3 PROTOCOL DEVIATIONS

A protocol deviation is any noncompliance with the clinical trial protocol, International Conference on Harmonization Good Clinical Practice (ICH GCP), or Manual of Procedures (MOP) requirements. The noncompliance may be either on the part of the participant, the investigator, or the study site staff. As a result of deviations, corrective actions are to be developed by the site and implemented promptly.

These practices are consistent with ICH GCP:

- 4.5 Compliance with Protocol, sections 4.5.1, 4.5.2, and 4.5.3
- 5.1 Quality Assurance and Quality Control, section 5.1.1
- 5.20 Noncompliance, sections 5.20.1, and 5.20.2.

It is the responsibility of the site investigator to use continuous vigilance to identify and report deviations within 10 working days of identification of the protocol deviation, or within 5 working days of the scheduled protocol-required activity. All deviations must be addressed in study source documents, reported to the sponsor or their designee. Protocol deviations must be sent to the reviewing IEC per their policies. The site investigator is responsible for knowing and adhering to the reviewing IEC requirements.

### 9.4 STATISTICAL ANALYSES

#### 9.4.1 GENERAL APPROACH

In general, continuous data will be summarized with descriptive statistics (number of patients, mean, standard deviation, median, minimum, and maximum) and will be analyzed using analysis of variance (ANOVA) techniques or 2-sample t-tests for between-group comparisons, and paired t-tests for within-group analyses. Categorical variables will be summarized by sample size (N), frequency count, and percent, and they will be analyzed using Pearson's chi-square test or Fisher's exact test (if the expected cell count is less than 5 in 25% or more of the cells). Ordinal variables will be analyzed using the Wilcoxon rank-sum test for between-treatment comparisons and the sign-rank test for within-treatment comparisons.

*Efficacy (MGD):*

*Primary Sign for MGD:*

- Change from Baseline to month 3 in meibum gland secretion score (MGS) (0 to 45 scale)

*Primary Symptom for MGD:*

- Change from Baseline to month 3 in Total OSDI

*Other Efficacy Measures:*

- Change from Baseline to day14, month 1 and month 1.5 in MGS (0 to 45 scale)
- MGS score (0 to 45 scale) at each visit
- Proportion of patients with a MGS score > 12 at each visit
- Change from Baseline to day14, month 1, month 1.5 and month 3 in the number of Meibomian Glands Yielding Liquid Secretion (MGYLS) (0 to 15 scale)
- MGYLS (0 to 15 scale) at each visit
- Change from Baseline to day 14, month 1, month 1.5, and month 3 in TBUT
- TBUT at each visit
- Proportion of patients with a TBUT score > 5 at each visit
- Change from Baseline to day 14, month 1, month 1.5 and month 3 in Standard Patient Evaluation of Eye Dryness (SPEED)
- SPEED at each visit
- Proportion of patients with a SPEED < 6 at each visit
- Change from Baseline to day 14, month 1, month 1.5 and month 3 in average visual analogue scale (VAS)
- Average VAS at each visit
- Change from Baseline to day 14, month 1, month 1.5 and month 3 in worst VAS
- Worst VAS at each visit
- Change from Baseline to day 14, month 1 and month 1.5 in Total OSDI
- Total OSDI, OSDI sub-scales, and individual items from the OSDI across visits
- Proportion of patients with a Total OSDI change from baseline > 4.5, the known minimally important clinical difference (MICD) for early to moderate disease, at month 3
- Proportion of patients with a Total OSDI < 13 at each visit
- Number of expressible glands yielding clear meibum at day14, month 1, month 1.5, and month 3
- Eyelid margin erythema/telangiectasias at day14, month 1, month 1.5, and month 3
- Corneal and conjunctival staining (0 to 5 scale) at each visit

*Safety:* Safety measures will be analyzed using the safety population. Medical Dictionary for Regulatory Activities (MedDRA) nomenclature will be used to code adverse events. Incidence rates of each treatment-emergent adverse event will be summarized by primary system organ class and preferred term. Summary tables will be generated for all treatment-emergent adverse events regardless of causality as well as for those considered to be treatment-related.

